Eight single-agent Novartis sponsored trials have or are being conducted in various advanced malignancies. Five Phase I studies evaluated several escalating doses with either weekly or daily administration (Studies C2101/02, C2106, C2107, C1101) of everolimus with the objective to identify an optimal regimen and dosage, based on safety, pharmacokinetics and knowledge of the drug's molecular effects on various tumors. The 10 mg/day and 50-70 mg/week dosages were proposed for further studies, when using everolimus as a single agent, and as a target maximum dose in combination studies. In addition the Phase I studies, conducted in prostate cancer (Study C2106) and in Japanese patients with advanced cancers (Study C1101), evaluated the safety and the molecular changes in tumor, associated with the administration of everolimus. Two Phase II monotherapy studies were designed to evaluate the safety and efficacy of a single dose of 10 mg administered daily including Study C2235 in advanced NSCLC (n=81) and Study C2239 in advanced pancreatic neuroendocrine tumors (n=160). A Phase III, randomized, double blind, placebo controlled study in patients with mRCC who progressed on a VEGFr TKI demonstrated that everolimus, administered daily at an oral dose of 10 mg, was superior to placebo for the primary endpoint of progression free survival. Median PFS was prolonged from 1.9 months for patients receiving placebo to 4.9 months for everolimus treated patients, assessed by central independent review blinded to clinical data (hazard ratio 0.33, 95% CI 0.25-0.43, p<0.001) (Kay et al, 2009). On 30 March 2009 everolimus was approved for use in the United States for the treatment of patients with advanced renal cell carcinoma after failure of treatment with sunitinib or sorafenib. Overall, the most frequent adverse effects suspected to be related to everolimus have been stomatitis, rash, anemia, fatigue, asthenia, diarrhea, anorexia, nausea, hypercholesterolemia, mucosal inflammation, vomiting, hypertriglyceridemia, cough, peripheral edema, dry skin, epistaxis, pruritus and dyspnea. The most common Grade 3 or 4 adverse reactions suspected to be related to treatment were anemia, infections, hyperglycemia, stomatitis, fatigue, lymphopenia, hypercholesterolemia, pneumonitis, and elevated gammaglutamyltransferase concentrations. Non-infectious low-Grade (Grade 1/2) pneumonitis has led to development of treatment guidelines for the disorder ([Section 6, Table 5](#)). The primary DLT has been severe (Grade 3) stomatitis, and occasionally fatigue, hyperglycemia, and neutropenia.

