| Grade 4 Neutropenia (neutrophils $< 0.5 \times 10^9/L$) | Interrupt study drug until recovery to grade ≤ 1 (neutrophils $\geq 1.5 \times 10^9/L$). Then resume study drug at the lower dose level. If grade 3 or grade 4 neutropenia occurs despite this dose reduction, discontinue study drug. |
| Grade 3 febrile neutropenia (not life-threatening) | Interrupt study drug until resolution of fever and neutropenia to grade ≤ 1 . Hold further study drug until the ANC $\geq 1,500/mm^3$ and fever has resolved. Then resume study drug at the lower dose level. If febrile neutropenia recurs, discontinue study drug. |
| Grade 4 febrile neutropenia (life-threatening) | Discontinue study drug. |
| Any hematological or non-hematological toxicity requiring interruption for ≥ 4 weeks | Discontinue study drug. |

* Grade 3 hyperlipidemia (hypercholesterolemia and/or hypertriglyceridemia) should be managed using medical therapies.

Management of stomatitis/oral mucositis/mouth ulcers

Stomatitis/oral mucositis/mouth ulcers due to study drug should be treated using local supportive care. Please note that investigators in earlier trials have described the oral toxicities associated with study drug as mouth ulcers, rather than mucositis or stomatitis. If your examination reveals mouth ulcers rather than a more general inflammation of the mouth, please classify the adverse event as such. Please follow the paradigm below for treatment of stomatitis/oral mucositis/mouth ulcers:

1. For mild toxicity (Grade 1), use conservative measures such as **non-alcoholic mouth wash or salt water (0.9%) mouth wash** several times a day until resolution.
2. For more severe toxicity (Grade 2 in which case patients have pain but are able to maintain adequate oral alimentation, or Grade 3 in which case patients cannot maintain adequate oral alimentation), the suggested treatments are **topical analgesic**

mouth treatments (i.e., local anesthetics such as benzocaine, butyl aminobenzoate, tetracaine hydrochloride, menthol, or phenol) with or without topical corticosteroids, such as triamcinolone oral paste 0.1% (Kenalog in Orabase®).

3. Agents containing hydrogen peroxide, iodine, and thyme derivatives may tend to worsen mouth ulcers. It is preferable to avoid these agents.

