4. Antifungal agents must be avoided unless a fungal infection is diagnosed. In particular, systemic imidazole antifungal agents (ketoconazole, fluconazole, itraconazole, etc.) should be avoided in all patients due to their strong inhibition of metabolism of study drugs, thereby leading to higher drug level exposures. Therefore, topical antifungal agents are preferred if an infection is diagnosed. Similarly, antiviral agents such as acyclovir should be avoided unless a viral infection is diagnosed. Note: Stomatitis/oral mucositis should be appropriately graded using the functional grading given on the NCI-CTC for adverse events, version 4.0.

Management of hyperlipidemia and hyperglycemia

Treatment of hyperlipidemia should take into account the pre-treatment status and dietary habits. Blood tests to monitor hyperlipidemia must be taken in the fasting state. Grade 2 hypercholesterolemia (> 300 mg/dL or 7.75 mmol/L) or Grade 2 hypertriglyceridemia (>2.5 x ULN) should be treated with a 3-hydroxy-3-methyl-glutaryl (HMG)-CoA reductase inhibitor (e.g., atorvastatin, pravastatin) or appropriate lipid-lowering medication, in addition to diet. Patients should be monitored clinically and through serum biochemistry for the development of rhabdomyolysis and other adverse events as required in the product label/data sheets for HMG-CoA reductase inhibitors.

Note: Concomitant therapy with fibrates and an HMG-CoA reductase inhibitor is associated with an increased risk of a rare but serious skeletal muscle toxicity manifested by rhabdomyolysis, markedly elevated creatine kinase (CPK) levels and myoglobinuria, acute renal failure and sometimes death. The risk versus benefit of using this therapy should be determined for individual patients based on their risk of cardiovascular complications of hyperlipidemia.

Grade 3 **hyperglycemia** has been observed in patients receiving everolimus therapy. It is suggested that optimal glucose control should be achieved before starting a patient on everolimus and should be monitored during everolimus therapy.

Table 5 - Management of non-infectious pneumonitis

| Worst Grade Pneumonitis | Required Investigations | Management of Pneumonitis | Everolimus Dose Adjustment |
|-------------------------|---|---|--|

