7.1 Comprehensive Adverse Events and Potential Risks Lists (CAEPRs)

7.1.1 CAEPR for MK-2206

Comprehensive Adverse Events and Potential Risks list (CAEPR) for MK-2206 (NSC 749607)

The Comprehensive Adverse Events and Potential Risks list (CAEPR) provides a single list of reported and/or potential adverse events (AE) associated with an agent using a uniform presentation of events by body system. In addition to the comprehensive list, a subset, the Specific Protocol Exceptions to Expedited Reporting (SPEER), appears in a separate column and is identified with bold and italicized text. This subset of AEs (SPEER) is a list of events that are protocol specific exceptions to expedited reporting to NCI (except as noted below). Refer to the 'CTEP, NCI Guidelines: Adverse Event Reporting Requirements' http://ctep.cancer.gov/protocolDevelopment/electronic_applications/docs/aeguidelines.pdf for further clarification. Frequency is provided based on 245 patients. Below is the CAEPR for MK-2206.

NOTE: Report AEs on the SPEER **ONLY IF** they exceed the grade noted in parentheses next to the AE in the SPEER. If this CAEPR is part of a combination protocol using multiple investigational agents and has an AE listed on different SPEERs, use the lower of the grades to determine if expedited reporting is required.

Version 2.2, June 16, 2015¹

| Adverse Events with Possible Relationship to MK-2206 (CTCAE 4.0 Term) [n= 245] | | | Specific Protocol Exceptions to Expedited Reporting (SPEER) |
|--|--|------------------------|--|
| Likely (>20%) | Less Likely (<=20%) | Rare but Serious (<3%) | |
| BLOOD AND LYMPHATIC SYSTEM DISORDERS | | | |
| | Anemia | | |
| CARDIAC DISORDERS | | | |
| | Sinus bradycardia | | Sinus bradycardia (Gr 2) |
| GASTROINTESTINAL DISORDERS | | | |
| | Diarrhea | | Diarrhea (Gr 3) |
| | Mucositis oral | | Mucositis oral (Gr 3) |
| Nausea | | | Nausea (Gr 2) |
| | Vomiting | | Vomiting (Gr 3) |
| GENERAL DISORDERS AND ADMINISTRATION SITE CONDITIONS | | | |
| Fatigue | | | Fatigue (Gr 3) |
| | Fever | | Fever (Gr 2) |
| INVESTIGATIONS | | | |
| | Alanine aminotransferase increased | | |
| | Alkaline phosphatase increased | | |
| | Aspartate aminotransferase increased | | |
| | Creatinine increased | | |
| | Electrocardiogram QT corrected interval prolonged | | Electrocardiogram QT corrected interval prolonged (Gr 2) |
| | Hemoglobin increased | | |

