¹This table will be updated as the toxicity profile of the agent is revised. Updates will be distributed to all Principal Investigators at the time of revision. The current version can be obtained by contacting [contact]. Your name, the name of the investigator, the protocol and the agent should be included in the e-mail.

²Includes diarrhea, enteritis, enterocolitis, colitis, defecation urgency, and steatorrhea.

³Includes stomatitis, aphthous stomatitis, gingival pain/swelling/ulceration, glossitis, glossodynia, lip ulceration, mouth ulceration, tongue ulceration, and mucosal inflammation.

⁴Infection includes all 75 infection sites under the INFECTIONS AND INFESTATIONS SOC.

⁵Everolimus delays wound healing and increases the occurrence of wound-related complications like wound dehiscence, wound infection, incisional hernia, lymphocele, and seroma.

⁶Hyperglycemia may result in either exacerbation of or development new onset diabetes mellitus.

⁷Includes pneumonitis, interstitial lung disease, lung infiltration, pulmonary alveolar hemorrhage, pulmonary toxicity, alveolitis, pulmonary fibrosis, and restrictive pulmonary disease.

⁸Patients taking concomitant ACE inhibitor therapy may be at increased risk for angioedema

⁹Includes agitation, anxiety, panic attack, aggression, abnormal behavior, and obsessive compulsive disorder.

Adverse events reported on Everolimus (RAD-001) trials, but for which there is insufficient evidence to suggest that there was a reasonable possibility that Everolimus (RAD-001) caused the adverse event:

BLOOD AND LYMPHATIC SYSTEM DISORDERS - Blood and lymphatic system disorders - Other (thrombotic microangiopathy)

CARDIAC DISORDERS - Atrial fibrillation; Cardiac disorders - Other (myocardial abnormality); Chest pain - cardiac; Heart failure; Left ventricular systolic dysfunction; Myocardial infarction; Sinus bradycardia; Sinus tachycardia; Supraventricular tachycardia

ENDOCRINE DISORDERS - Endocrine disorders - Other (increased blood follicle stimulating hormone [FSH] levels); Endocrine disorders - Other (increased blood luteinizing hormone [LH] levels); Endocrine disorders - Other (low testosterone); Hypothyroidism

EYE DISORDERS - Blurred vision; Conjunctivitis; Keratitis

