7.2 Adverse Event Characteristics

- CTCAE term (AE description) and grade: The descriptions and grading scales found in the revised NCI Common Terminology Criteria for Adverse Events (CTCAE) version 4.0 will be utilized until March 31, 2018 for AE reporting. CTCAE version 5.0 will be utilized for AE reporting beginning April 1, 2018. All appropriate treatment areas should have access to a copy of the CTCAE version 5.0. A copy of the CTCAE version 5.0 can be downloaded from the CTEP web site http://ctep.cancer.gov/protocolDevelopment/electronic_applications/ctc.htm.
- ‘Expectedness’: AEs can be ‘Unexpected’ or ‘Expected’ (see [Section 7.1](#) above) for expedited reporting purposes only. ‘Expected’ AEs (the ASael) are ***bold and italicized*** in the CAEPR ([Section 7.1.1](#)).
- **Attribution** of the AE:
 - Definite – The AE *is clearly related* to the study treatment.
 - Probable – The AE *is likely related* to the study treatment.
 - Possible – The AE *may be related* to the study treatment.

- Unlikely – The AE is *doubtfully related* to the study treatment.
- Unrelated – The AE is *clearly NOT related* to the study treatment.

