13.4 Statistical Analysis Plan

The primary endpoint, progression-free survival (PFS), is defined as the time interval between date of treatment and date of disease progression, date of death or last follow-up date, whichever occurred first. The probability of PFS be estimated using the Kaplan-Meier method and will be compared between the two treatment arms using stratified log-rank test. Patients' safety data will be summarized by treatment arm, category, severity and relevance.

For secondary analyses, the Kaplan-Meier method will be used to estimate overall survival (OS) and time to failure (TTF), and stratified log-rank test will be used to compare between the two treatment arms. The OS is defined as the time interval between the date of treatment and the date of death or last follow-up, whichever occurred first. The TTF is defined as the time interval between the date of treatment and the date of disease progression, date of death, date of treatment discontinuation due to severe toxicity or last follow-up date, whichever occurred first. Overall response (OR) is defined as CR+PR and logistic regression model will be fit to assess the effect of treatment on the rate of OR.

Since the correlative studies being performed are by nature exploratory, and have not been

performed before in patients with RCC receiving mTOR inhibitors or AKT inhibitors, powering of these endpoints is not possible. Clinical benefit is defined as CR+PR+SD and again, we will fit logistic regression models to assess the effects of treatment, AKT activation, circulating cytokines and angiogenic factors, and karyotype on clinical benefit. The interaction effect between treatment and these exploratory factors will also be evaluated.

For virtual karyotyping, technique specific statistical analyses are outlined in [Appendix G](#).

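### Section 6.2 asks, for everolimus only, that mouth ulcers be classified separately from general oral inflammation; with no grouping rule in 13.4, *Mucositis oral* may be under-counted on that arm

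*Combined protocol and SAP*

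**What the plan says.** Section 6.2 (Everolimus), under management of stomatitis, oral mucositis and mouth ulcers, first notes that "investigators in earlier trials have described the oral toxicities associated with study drug as mouth ulcers, rather than mucositis or stomatitis". It then tells the investigator: "If your examination reveals mouth ulcers rather than a more general inflammation of the mouth, please classify the adverse event as such". A later note in the same list adds: "Stomatitis/oral mucositis should be appropriately graded using the functional grading given on the NCI-CTC for adverse events, version 4.0".

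Section 6.1 (MK-2206) covers hyperglycemia and rash. It says nothing on recording oral events, although *Mucositis oral* is on the MK-2206 list in 7.1.1 and mild to moderate mucositis is reported in 2.2.

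In 7.1.2, footnote 3 to *Mucositis oral* lists what the term includes. The list starts with stomatitis and ends with "lip ulceration, mouth ulceration, tongue ulceration, and mucosal inflammation". The MK-2206 list carries the same term without a footnote.

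Section 7.2 sets CTCAE terms and grades for adverse event reporting without distinguishing the arms. Version 4.0 applies first, and "CTCAE version 5.0 will be utilized for AE reporting beginning April 1, 2018".

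The planned analysis, in 13.4, is that "safety data will be summarized by treatment arm, category, severity and relevance".

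**The concern.** The sentence in 6.2 governs how an event is recorded, not how it is treated, and it applies to one arm of an open-label trial. A site that follows it literally would keep ulcers apart from mucositis on everolimus. With no such instruction for MK-2206, the same lesion there could simply be entered as *Mucositis oral*.

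This falls on a toxicity that matters for everolimus. Section 2.3.4 states: "The primary DLT has been severe (Grade 3) stomatitis". The risk lists put oral mucositis above 20% for everolimus and at or below 20% for MK-2206. Safety of MK-2206 is among the primary objectives in 1.1, and everolimus is its only comparator in the by-arm tables. If ulcers were recorded apart on everolimus alone, the error would run one way: fewer everolimus events under *Mucositis oral*, and a less favourable relative picture for MK-2206 on that row.

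**Working it through.** The plan gives no figure to reproduce, so the check is first a comparison of texts and then an illustration on assumed inputs.

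**1. The texts side by side**

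| Place | Arm | Treatment of mouth ulcers |
|---|---|---|
| 6.2, classification sentence | Everolimus | Separate from general inflammation, if that is what examination shows |
| 6.2, grading note | Everolimus | Names stomatitis and oral mucositis only |
| 7.1.2, footnote 3 | Everolimus | Inside *Mucositis oral* |
| 6.1 | MK-2206 | No instruction |
| 7.1.1 | MK-2206 | *Mucositis oral* listed, contents not defined |
| 7.2 | Both | CTCAE terms |
| 13.4 | Both | No grouping rule |

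Section 6.2 separates what footnote 3 combines, and nothing says which governs the recorded term.

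**2. Whether the data system allows a split.** It does. The data schedule in Appendix K requires symptom text when an *other* adverse event is used, so a site can enter an event outside the listed terms. A site can equally enter *Mucositis oral* and describe the ulcers. The documents do not settle which will happen.

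**3. Illustration of size.** From the documents: 35 everolimus patients (13.2). Assumed: true oral toxicity rate p, and share f of those patients recorded only as mouth ulcers.

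Recorded count under *Mucositis oral*, not pooled = 35 × p × (1 − f).

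| p | f = 0 | f = 25% | f = 50% | f = 75% |
|---|---|---|---|---|
| 20% | 7.0 | 5.25 | 3.5 | 1.75 |
| 30% | 10.5 | 7.9 | 5.25 | 2.6 |
| 40% | 14.0 | 10.5 | 7.0 | 3.5 |
| 50% | 17.5 | 13.1 | 8.75 | 4.4 |

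If the footnote 3 terms are pooled, the count is the f = 0 column whatever f is.

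**4. Effect on the difference between arms.** Assume true rates of 30% on everolimus and 15% on MK-2206. These fit the lists' bands (>20% and ≤20%) but are not given there.

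- Only everolimus ulcers recorded separately: difference = 30(1 − f) − 15. For f = 10%, 30% and 50% this is 12, 6 and 0 points, against a true 15. Patients lost from the term: 10.5 × f = 1.05, 3.15 and 5.25.
- Same share recorded separately in both arms: difference = 15(1 − f), that is 13.5, 10.5 and 7.5 points.
- Pooled in both arms: 15 points for any f.

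**5. What the coding can reach.** Section 13.4 plans a descriptive safety summary with no test of oral mucositis. The stopping rule in 13.1 monitors the MK-2206 arm only, counting Grade 3 or greater toxicity that requires discontinuation. PFS does not use these data. A total by organ class would include the event under either label.

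**The case against.** The strongest reply is that the passages can coexist. The 6.2 sentence is conditional: general inflammation is still recorded as stomatitis or mucositis, and only a finding of ulcers is named as such. A site could describe ulcers in the chart and report them under *Mucositis oral*, satisfying 6.2, 7.2 and footnote 3 together. Appendix K has auditors check for the appropriate toxicity-criteria term. The patients would in any case still appear in the by-arm table, under a neighbouring term.

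Much of this stands: the split is possible, not established. It does not close the point, because 6.2 says to classify the event, not merely to describe it. Footnote 3 serves the risk list and expedited reporting and is not an analysis rule, and 13.4 does not adopt it.

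A reader might infer four stronger things that the documents do not support:

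- That 6.2 relabels everolimus oral toxicity in general. The condition on the examination finding rules that out.
- That ulcers drop out of the expedited-reporting exception. Footnote 3 is attached to that entry itself in 7.1.2, so mouth ulceration is expressly inside it.
- That this is where the arms are expected to differ most. Anemia and diarrhea show the same pattern of >20% on everolimus and ≤20% on MK-2206, and hyperglycemia shows the reverse.
- That the remark about earlier trials implies a large ulcer share. It gives no proportion.

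**Conclusion.** The point holds as a low-severity inconsistency in adverse event coding. Section 6.2 conflicts with footnote 3 and with the common terminology in 7.2, for one arm only, and 13.4 has nothing to absorb the difference. Everolimus oral toxicity may therefore be under-counted under *Mucositis oral* in the descriptive table.

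Whether it is under-counted, and by how much, cannot be known from the documents. The loss of about 1 to 5 patients, and the shrinkage of a 15-point difference to between 12 and 0 points, rest wholly on assumed rates of 30% and 15%, ulcer shares of 10% to 50%, no pooling, and no separate recording of ulcers on MK-2206. Organ-class totals, formal tests, the toxicity stopping rule, PFS and the expedited-reporting definition are not affected.

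**What to change.** Two changes:

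1. Reconcile 6.2 with 7.2 and footnote 3 through one recording instruction for both arms, placed in 7.2 or repeated in 6.1 and 6.2: *record stomatitis, oral mucositis and mouth ulcers under the CTCAE term Mucositis oral, with lesion type as free text.*
2. Add to 13.4: *the by-arm safety table pools the terms in footnote 3 of the everolimus CAEPR into one oral term for both arms, counting each patient once at the worst grade; ulcers may be shown as a sub-row.*

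The second change also repairs data already collected, provided that free-text entries are searched in both arms. The cost is two sentences and a small regrouping step when the table is built. The optional sub-row keeps the separate view of ulcers. No dose or treatment rule changes.

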7. ADVERSE EVENTS: LIST AND REPORTING REQUIREMENTS

Adverse event (AE) monitoring and reporting is a routine part of every clinical trial. The following list of AEs ([Section 7.1](#)) and the characteristics of an observed AE ([Section 7.2](#)) will determine whether the event requires expedited (via CTEP-AERS) reporting in addition to routine reporting.

7.1 Comprehensive Adverse Events and Potential Risks Lists (CAEPRs)

7.1.1 CAEPR for MK-2206

Comprehensive Adverse Events and Potential Risks list (CAEPR) for MK-2206 (NSC 749607)

The Comprehensive Adverse Events and Potential Risks list (CAEPR) provides a single list of reported and/or potential adverse events (AE) associated with an agent using a uniform presentation of events by body system. In addition to the comprehensive list, a subset, the Specific Protocol Exceptions to Expedited Reporting (SPEER), appears in a separate column and is identified with bold and italicized text. This subset of AEs (SPEER) is a list of events that are protocol specific exceptions to expedited reporting to NCI (except as noted below). Refer to the 'CTEP, NCI Guidelines: Adverse Event Reporting Requirements' http://ctep.cancer.gov/protocolDevelopment/electronic_applications/docs/aeguidelines.pdf for further clarification. Frequency is provided based on 245 patients. Below is the CAEPR for MK-2206.

NOTE: Report AEs on the SPEER **ONLY IF** they exceed the grade noted in parentheses next to the AE in the SPEER. If this CAEPR is part of a combination protocol using multiple investigational agents and has an AE listed on different SPEERs, use the lower of the grades to determine if expedited reporting is required.

Version 2.2, June 16, 2015¹

| Adverse Events with Possible Relationship to MK-2206 (CTCAE 4.0 Term) [n= 245] | | | Specific Protocol Exceptions to Expedited Reporting (SPEER) |
|--|--|------------------------|--|
| Likely (>20%) | Less Likely (<=20%) | Rare but Serious (<3%) | |
| BLOOD AND LYMPHATIC SYSTEM DISORDERS | | | |
| | Anemia | | |
| CARDIAC DISORDERS | | | |
| | Sinus bradycardia | | Sinus bradycardia (Gr 2) |
| GASTROINTESTINAL DISORDERS | | | |
| | Diarrhea | | Diarrhea (Gr 3) |
| | Mucositis oral | | Mucositis oral (Gr 3) |
| Nausea | | | Nausea (Gr 2) |
| | Vomiting | | Vomiting (Gr 3) |
| GENERAL DISORDERS AND ADMINISTRATION SITE CONDITIONS | | | |
| Fatigue | | | Fatigue (Gr 3) |
| | Fever | | Fever (Gr 2) |
| INVESTIGATIONS | | | |
| | Alanine aminotransferase increased | | |
| | Alkaline phosphatase increased | | |
| | Aspartate aminotransferase increased | | |
| | Creatinine increased | | |
| | Electrocardiogram QT corrected interval prolonged | | Electrocardiogram QT corrected interval prolonged (Gr 2) |
| | Hemoglobin increased | | |
| | Investigations - Other (eosinophilia) | | Investigations - Other (eosinophilia) (Gr 2) |
| | Investigations - Other (insulin c-peptide increased) | | |
| | Lymphocyte count decreased | | Lymphocyte count decreased (Gr 4) |

| Adverse Events with Possible Relationship to MK-2206 (CTCAE 4.0 Term) [n= 245] | | | Specific Protocol Exceptions to Expedited Reporting (SPEER) |
|--|----------------------------|------------------------|---|
| Likely (>20%) | Less Likely (<=20%) | Rare but Serious (<3%) | |
| | Neutrophil count decreased | | Neutrophil count decreased (Gr 4) |
| | Platelet count decreased | | |
| | Weight loss | | |
| | White blood cell decreased | | White blood cell decreased (Gr 2) |
| METABOLISM AND NUTRITION DISORDERS | | | |
| | Anorexia | | Anorexia (Gr 2) |
| Hyperglycemia | | | Hyperglycemia (Gr 3) |
| | Hypocalcemia | | |
| | Hyponatremia | | |
| NERVOUS SYSTEM DISORDERS | | | |
| | Dysgeusia | | |
| | Headache | | Headache (Gr 2) |
| SKIN AND SUBCUTANEOUS TISSUE DISORDERS | | | |
| | Dry skin | | Dry skin (Gr 2) |
| | Pruritus | | Pruritus (Gr 2) |
| Rash maculo-papular | | | Rash maculo-papular (Gr 3) |

¹This table will be updated as the toxicity profile of the agent is revised. Updates will be distributed to all Principal Investigators at the time of revision. The current version can be obtained by contacting [contact]. Your name, the name of the investigator, the protocol and the agent should be included in the e-mail.

Adverse events reported on MK-2206 trials, but for which there is insufficient evidence to suggest that there was a reasonable possibility that MK-2206 caused the adverse event:

- BLOOD AND LYMPHATIC SYSTEM DISORDERS** - Febrile neutropenia; Hemolysis; Hemolytic uremic syndrome; Leukocytosis
- CARDIAC DISORDERS** - Atrioventricular block complete; Left ventricular systolic dysfunction; Myocardial infarction; Palpitations; Ventricular arrhythmia
- EAR AND LABYRINTH DISORDERS** - Vertigo
- ENDOCRINE DISORDERS** - Hypothyroidism
- EYE DISORDERS** - Blurred vision; Conjunctivitis; Dry eye; Extraocular muscle paresis; Eye disorders - Other (blepharitis); Eye disorders - Other (eye swelling); Eye disorders - Other (foreign body sensation in eyes); Eye disorders - Other (iritis); Eye disorders - Other (mydriasis); Eye disorders - Other (visual acuity reduced); Eye pain; Floaters; Keratitis; Photophobia; Retinal detachment; Uveitis
- GASTROINTESTINAL DISORDERS** - Abdominal distension; Abdominal pain; Ascites; Cheilitis; Colonic perforation; Constipation; Dry mouth; Dyspepsia; Dysphagia; Gastritis; Gastrointestinal disorders - Other (oropharyngeal pain); Lip pain; Toothache
- GENERAL DISORDERS AND ADMINISTRATION SITE CONDITIONS** - Chills; Edema face; Edema limbs; Flu like symptoms; General disorders and administration site conditions - Other (throat tightness); Injection site reaction; Irritability; Localized edema; Non-cardiac chest pain; Pain
- IMMUNE SYSTEM DISORDERS** - Allergic reaction
- INFECTIONS AND INFESTATIONS** - Infections and infestations - Other (herpetic vesicular rash [due to herpes zoster infection]); Infections and infestations - Other (oral herpes); Lung infection; Nail infection; Paronychia; Pharyngitis; Rhinitis infective; Sepsis; Sinusitis; Skin infection; Urinary tract infection
- INJURY, POISONING AND PROCEDURAL COMPLICATIONS** - Fall
- INVESTIGATIONS** - Activated partial thromboplastin time prolonged; Blood bilirubin increased; INR increased; Investigations - Other (blood LDH increased); Investigations - Other (hyperinsulinemia); Lipase increased; Serum amylase increased; Weight gain

METABOLISM AND NUTRITION DISORDERS - Dehydration; Hypercalcemia; Hyperkalemia; Hypermagnesemia; Hypoalbuminemia; Hypokalemia; Hypomagnesemia; Hypophosphatemia
MUSCULOSKELETAL AND CONNECTIVE TISSUE DISORDERS - Arthralgia; Back pain; Bone pain; Generalized muscle weakness; Myalgia; Neck pain; Pain in extremity
NERVOUS SYSTEM DISORDERS - Akathisia; Dizziness; Encephalopathy; Lethargy; Presyncope; Reversible posterior leukoencephalopathy syndrome; Seizure; Syncope; Tremor
PSYCHIATRIC DISORDERS - Anxiety; Confusion; Depression; Insomnia
RENAL AND URINARY DISORDERS - Acute kidney injury; Proteinuria; Renal and urinary disorders - Other (renal tubular necrosis); Renal and urinary disorders - Other (glucose urine present); Urinary incontinence; Urinary tract pain
REPRODUCTIVE SYSTEM AND BREAST DISORDERS - Gynecomastia; Vaginal hemorrhage; Vaginal perforation
RESPIRATORY, THORACIC AND MEDIASTINAL DISORDERS - Bronchial obstruction; Cough; Dyspnea; Epistaxis; Hypoxia; Pneumonitis; Pulmonary edema; Respiratory failure; Sore throat
SKIN AND SUBCUTANEOUS TISSUE DISORDERS - Alopecia; Erythema multiforme; Erythroderma; Hyperhidrosis; Palmar-plantar erythrodysesthesia syndrome; Photosensitivity; Purpura; Rash acneiform; Skin and subcutaneous tissue disorders - Other (skin irritation); Stevens-Johnson syndrome; Urticaria
VASCULAR DISORDERS - Hematoma; Hypertension; Hypotension; Thromboembolic event

Note: MK-2206 in combination with other agents could cause an exacerbation of any adverse event currently known to be caused by the other agent, or the combination may result in events never previously associated with either agent.

